#### 2.3 Use of study populations

Demographics and baseline characteristics will be reported separately for:

- ITT population
- PP population

Job Number: 1555 Customer Reference: Study ID: 020221 SAP Version: 1.0

- Pseudo-progression cohort
- Informational cohort

Efficacy data will be reported separately for:

- ITT population
- PP population
- Pseudo-progression cohort
- Informational cohort

#### Note:

- 1. The conditional survival endpoint is calculated in patients reaching the chosen threshold.
- 2. Subgroup analyses will also be conducted.
- 3. The efficacy analysis for the Informational cohort will not be comparative, as there is only one arm, and will only include descriptive statistics.

Safety data will be reported for the Safety population.

#### 2.4 External comparator populations

Systematic literature reviews have been conducted by independent experts, followed by consultation with neuro-oncology experts, to identify relevant studies in newly diagnosed GBM and in recurrent GBM respectively, to provide comparator control populations as described above. Two separate reports (one for newly diagnosed GBM and one for recurrent GBM), detailing search terms, databases searched and all other relevant details, are provided as Appendices.

# **Section 3:** Endpoints

#### 3.1 Study endpoints based on survival and progression

Table 2 summarises the endpoints defined by survival and progression.

Table 2: Endpoints

Primary: DCVax®-L Study 020221² vs external controls³ in newly diagnosed GBM         OS       ITT & PP       Hazard ratio; landmarks Hazard ratio; landmarks       α-exhaustive extension of the fallback lall back landmarks         OS       ITT & PP subgroups       Hazard ratio; landmarks       [8] procedure, plus hierarchy         Secondary: DCVax®-L Study 020221 crossover cohorts vs external controls⁶ recurrent GBM       Hazard ratio; landmarks         OS       Placebo crossover cohort       Cox PH       Hazard ratio; landmarks         Secondary: Internal to Study 020221         CPFS²       ITT & PP       Cox PH       Hazard ratio; landmarks         PFS       ITT & PP       Rarrison procedure for log rank test       Hazard ratio; landmarks         Sensitivity analyses: Internal to Study 020221         OS       ITT & PP       Cox PH       Hazard ratio; landmarks         PFS       ITT & PP       Cox PH       Hazard ratio; landmarks         OS       ITT & PP       Hazard ratio; landmarks         PFS       ITT & PP biomarker subgroup       Hazard ratio; landmarks         Exploratory: Internal to Study 020221       Hazard ratio; landmarks         TTP9       ITT       Hazard ratio; landmarks	Endpoint	Populations Model		Estimator	Multiplicity 			
CS\$ ITT & PP  COX PH4  Agard ratio; landmarks  Secondary: DCVax®-L Study 020221 crossover cohorts vs external controls6 recurrent GBM Placebo crossover cohort  COX PH  Hazard ratio; landmarks  PFS ITT & PP  COX PH  Hazard ratio; landmarks  Sensitivity analyses: Internal to Study 020221  OS ITT & PP  COX PH  Hazard ratio; landmarks  FFS ITT & PP  COX PH  Hazard ratio; landmarks  FFS ITT & PP  COX PH  Hazard ratio; landmarks  FFS ITT & PP biomarker subgroup  Hazard ratio; landmarks	Primary: D	Primary: DCVax®-L Study 020221  vs external controls  in newly diagnosed GBM						
CSS ITT & PP  COX PH4  Hazard ratio Hazard ratio; landmarks  [8] procedure, plus hierarchy  Secondary: DCVax®-L Study 020221 crossover cohorts vs external controls6 recurrent GBM  Placebo crossover cohort  COX PH  Hazard ratio; landmarks  Secondary: Internal to Study 020221  CPFS7 ITT & PP  COX PH  Hazard ratio; landmarks  PFS ITT & PP  COX PH  Hazard ratio; landmarks  FFS ITT & PP  COX PH  Hazard ratio; landmarks	OS	ITT & PP		Hazard ratio; landmarks	,			
OS ITT & PP subgroups  Secondary: DCVax®-L Study 020221 crossover cohorts vs external controls6 recurrent GBM OS Placebo crossover cohort  Cox PH  Hazard ratio; landmarks  PFS ITT & PP Cox PH  Hazard ratio; landmarks  Secondary: Internal to Study 020221  CPFS7 ITT & PP Cox PH Hazard ratio; landmarks  PFS ITT & PP Karrison procedure for log rank test  Sensitivity analyses: Internal to Study 020221  OS ITT & PP Cox PH Hazard ratio; landmarks  PFS ITT & PP Cox PH Hazard ratio; landmarks  PFS ITT & PP biomarker subgroup  Hazard ratio; landmarks  Hazard ratio; landmarks  Hazard ratio; landmarks  Hazard ratio; landmarks	CS⁵	ITT & PP	Cox PH 	Hazard ratio	the fallback			
OS Placebo crossover cohort Cox PH Hazard ratio; landmarks  Secondary: Internal to Study 020221  CPFS  ITT & PP Cox PH Hazard ratio; landmarks  PFS ITT & PP Karrison Hazard ratio; landmarks  OS ITT & PP PO	OS	ITT & PP subgroups	3	Hazard ratio; landmarks	procedure,			
Secondary: Internal to Study 020221  CPFS  ITT & PP	Secondary	: DCVax®-L Study 020221 crossover coh	orts vs external cont	rols  recurrent GBM	Hierarchy			
CPFS  ITT & PP  Cox PH  Hazard ratio; landmarks  PFS ITT & PP  Sensitivity analyses: Internal to Study 020221  OS ITT & PP  Cox PH  Hazard ratio; landmarks  Hazard ratio; landmarks  Cox PH  Hazard ratio; landmarks  Hazard ratio; landmarks  PFS ITT & PP  Hazard ratio; landmarks  FFS ITT & PP biomarker subgroup  Exploratory: Internal to Study 020221	OS	Placebo crossover cohort			5			
PFS ITT & PP Karrison procedure for log rank test  Sensitivity analyses: Internal to Study 020221  OS ITT & PP Cox PH Hazard ratio; landmarks  PFS ITT & PP Hazard ratio; landmarks  OS ITT & PP Hazard ratio; landmarks  PFS ITT & PP Hoiomarker subgroup Hazard ratio; landmarks  PFS ITT & PP biomarker subgroup Hazard ratio; landmarks  Exploratory: Internal to Study 020221	Secondary	: Internal to Study 020221			<del>_</del>			
OS ITT & PP procedure for log rank test  Sensitivity analyses: Internal to Study 020221  OS ITT & PP Cox PH Hazard ratio; landmarks  PFS ITT & PP Hazard ratio; landmarks  OS ITT & PP biomarker subgroup8 Hazard ratio; landmarks  PFS ITT & PP biomarker subgroup Hazard ratio; landmarks  Exploratory: Internal to Study 020221	cPFS 	ITT & PP	Cox PH	Hazard ratio; landmarks	5			
OS ITT & PP log rank test  Sensitivity analyses: Internal to Study 020221  OS ITT & PP Cox PH Hazard ratio; landmarks  PFS ITT & PP Hazard ratio; landmarks  OS ITT & PP biomarker subgroup  Hazard ratio; landmarks  PFS ITT & PP biomarker subgroup Hazard ratio; landmarks  Exploratory: Internal to Study 020221	PFS	ITT & PP	Karrison	Hazard ratio; landmarks	5			
OS ITT & PP Cox PH Hazard ratio; landmarks PFS ITT & PP Hazard ratio; landmarks OS ITT & PP biomarker subgroup  Hazard ratio; landmarks PFS ITT & PP biomarker subgroup Hazard ratio; landmarks  Exploratory: Internal to Study 020221	OS	ITT & PP		Hazard ratio; landmarks	5			
PFS ITT & PP Hazard ratio; landmarks OS ITT & PP biomarker subgroup  Hazard ratio; landmarks PFS ITT & PP biomarker subgroup Hazard ratio; landmarks  Exploratory: Internal to Study 020221	Sensitivity	analyses: Internal to Study 020221						
OS ITT & PP biomarker subgroup  Hazard ratio; landmarks PFS ITT & PP biomarker subgroup Hazard ratio; landmarks  Exploratory: Internal to Study 020221	OS	ITT & PP	Cox PH	Hazard ratio; landmarks	5			
PFS ITT & PP biomarker subgroup Hazard ratio; landmarks  Exploratory: Internal to Study 020221	PFS	ITT & PP		Hazard ratio; landmarks	5			
Exploratory: Internal to Study 020221	OS	ITT & PP biomarker subgroup 		Hazard ratio; landmarks	5			
	PFS	ITT & PP biomarker subgroup		Hazard ratio; landmarks	5			
TTP  ITT Hazard ratio; landmarks	Exploratory: Internal to Study 020221							
	TTP 	ITT		Hazard ratio; landmarks	5			

 $^{1}$   $\alpha$  5% 2 sided overall; accounting for interim analysis, final analysis to be conducted at  $\alpha$  2.409% 1 sided

<sup>2 Subjects randomized to DCVax®-L

<sup>3 Control arms from studies in newly diagnosed GBM identified in systematic literature review by independent experts, confirmed with independent neuro-oncology experts and further matched through MAIC

<sup>4 Analysis based on reconstructed IPD from external studies; if real data available then covariates included as available

<sup>5 Survival conditional on OS ≥ Observed median survival in Subjects randomized to DCVax®-L

<sup>6 Control arms from studies in recurrent GBM identified in systematic literature review by independent experts, confirmed with independent neuro-oncology experts and further matched through MAIC

<sup>7 Confirmed PFS

<sup>8 ITT population excluding: IDH-1 mutated and chromosome 1p19q co-deletions

<sup>9 Time to Progression

#### 3.1.1 Overall survival

For the Primary Endpoint, analyses #1 (ITT Population) and #3 (Pre-Specified Sub-Groups), OS will be calculated from the date of randomization to the date of death due to any cause. If a subject is not known to have died at the date of database lock, that subject will be censored at the date the subject was last known to be alive. For these Primary Endpoint analyses, OS for subjects randomized to DCVax®-L will be compared to closely matched, independently determined external controls.

For Secondary Endpoint #1 (Post-Progression OS), OS will be calculated from the date of progression to the date of death due to any cause for subjects originally randomized to placebo who received DCVax®-L after crossover. If a subject is not known to have died at the date of database lock, then the death for that subject will be censored at the date that the subject was last known to be alive. For these Post-Progression OS analyses, the subjects who received DCVax®-L after crossover will be compared to matched external controls obtained from trials in recurrent GBM.

For Secondary Endpoint #4 (OS in the ITT population), OS will be calculated from the date of randomization to the date of death due to any cause or date the subject was last known to be alive in the same manner as for the Primary Endpoint analysis #1, except that the OS for subjects randomized to DCVax®-L will be compared to Within-Study controls (i.e. subjects randomized to placebo).

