#### 3.2.3 Endpoints measured from surgery

The primary and secondary endpoints will be measured from the time of initial surgery ('is'), in addition to being measured from randomization as described above:

- isOS
- isCS
- isOS sub-groups
- isOS post-progression
- iscPFS
- isPFS
- isTTP

These endpoints are defined the same as for OS, CS, OS (sub-groups), OS (post-progression), cPFS, PFS, OS and TTP but with the time interval measured from initial surgery in place of randomization.

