#### 8.2.1 Primary analysis: simple proportional hazards model

The primary analysis will be a comparison between the reconstructed individual patient data for all subjects, pooled across the external studies, with the subjects who crossed over from the placebo arm and were treated with DCVax®-L post-progression. Cox's proportional hazards model will be used.

Median survival and a 95% confidence interval will be reported.

The hazard ratio (HR) and a 95% confidence interval will be reported, as well as the associated 2-sided p value. Estimates of survival probability at 6, 12, 18, 24, 30, 36, 42, 48, 54 and 60 months will be calculated (with 95% confidence intervals).

Kaplan-Meier estimates of the survival functions for the DCVax®-L population and the comparator population will be plotted.

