#### Primary Endpoint and Secondary Endpoint, Hypotheses, and Analytic Method

Primary: The primary objective of this study is to compare overall survival (OS) between patients randomized to DCVax-L and control patients from comparable, contemporaneous trials who received standard of care therapy only, in patients with newly diagnosed glioblastoma.

Hypothesis: Overall survival, measured from time of randomization, will be longer for patients in the DCVax-L cohort compared to patients who received standard of care in other, comparable, contemporaneous trials.

Analytic Method #1: Proportional hazards (Cox) regression.

Analytic Method #2: Conditional Survival analysis

Analytic Method #3: Overall Survival in specific subgroups

**Secondary**: The first secondary objective is to compare overall survival (OS) between patients randomized to placebo who received DCVax-L treatment following disease recurrence, and control patients from comparable, contemporaneous clinical trials, in patients with recurrent GBM.

Hypothesis: Overall survival, measured from time of disease progression, will be longer for patients in the placebo cohort who received treatment with DCVax-L upon disease progression, when compared to control patients from other comparable contemporaneous clinical trials who received best available care.

Analytic Method: Cox regression.

**Secondary**: The second secondary objective, confirmed progression-free survival (cPFS), is to compare confirmed disease progression (cPD) between subjects randomized to DCVax®-L and those randomized to Placebo within Study 020221.

Protocol: 020221, v7.0 23SEP2020 Page 3 of 55

Northwest Biotherapeutics, Inc. DCVax®-L, IND #10206

**Secondary**: The third secondary objective, PFS, is to compare progression-free survival between subjects randomized to DCVax®-L and those randomized to Placebo within Study 020221.

**Secondary**: The fourth secondary objective, OS, is to compare overall survival between subjects randomized to DCVax®-L and those randomized to Placebo within Study 020221.

**Secondary**: The fifth secondary objective is to compare tumor response between subjects randomized to DCVax®-L and those randomized to Placebo within Study 020221.

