## Treatment Schedule after Confirmed Progression and Crossover

• Patients will receive up to 10 DCVax-L injections at days 0, 10, 20, and months 2, 4, 8, 12, 18, 24 and 30. Day 0 is the date of the first immunization and must occur within 3 months of crossover (date of confirmation of disease progression). For the immunizations at days 10 and 20, and month 2, the variance may be ±2 days but the minimum interval between injections must be at least 9 days. For the immunizations at months 4, 8, 12, 18, 24, and 30 the variance can be ±1 week with a minimum interval of 6 weeks between injections. Vitals are recorded every 30 minutes for 2 hours post injection.

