#### Visit Windows for Schedule of Events:

Baseline Visit: two weeks (± 2 days) after completion of chemo-radiation

Time 0: target ≤7 days after Baseline Days 10 and 20, month 2: ± 2 days

Months 4, 8, 12, 18, 24, 30:  $\pm$  1 week, but >6 weeks between immunizations

All visits, including immunization dates, are calculated from day 0 (the date of the first immunization), and for the purposes of this protocol, a 28-day month is used for calculating visits.

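### Secondary Endpoint #1 counts survival from progression but includes only placebo patients who lived to a later first DCVax-L dose, so the waiting time is credited to DCVax-L unless the controls' clock also starts at progression

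*Combined protocol and SAP*

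**What the plan says.** SAP 3.1.1 defines the endpoint in one sentence with two parts. The clock: "OS will be calculated from the date of progression to the date of death due to any cause for subjects originally randomized to placebo". The population: "for subjects originally randomized to placebo who received DCVax®-L after crossover". SAP 1.2.2, 8.2 and 8.2.1 apply the same condition of having been treated, and so does the hypothesis in the protocol synopsis: "Overall survival, measured from time of disease progression, will be longer for patients in the placebo cohort who received treatment with DCVax-L upon disease progression".

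Protocol 8.4, on the treatment schedule after crossover, sets the timing of the first dose: "Day 0 is the date of the first immunization and must occur within 3 months of crossover (date of confirmation of disease progression". The same section makes crossover optional, requires independent verification of progression, and keeps patients who decline under survival follow-up.

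The test is a Cox model. SAP 8.2.1: "The primary analysis will be a comparison between the reconstructed individual patient data for all subjects, pooled across the external studies", against the treated placebo crossovers. SAP 8.2.3 adds matching-adjusted comparisons on up to five baseline characteristics (MGMT, KPS, age, sex, race). SAP 8.2.4 repeats the analyses for patients randomized to DCVax-L who received it again after progression, and for all crossovers. Under SAP 8.3.1 the secondary endpoints are tested in Table 2 order, each gated on its predecessor at 2.409%. Table 2 lists this endpoint first among them.

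**The concern.** Membership of the treated group is decided by an event, the first post-progression dose, that happens after the clock has started. Nobody in the group can die between progression and that dose, yet the interval counts as time at risk. This is immortal time. If a control study counts from its own enrolment or randomization, its patients have no matching protected interval.

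The 3-month window runs from confirmation of progression, whereas the SAP clock runs from progression, so the protected interval can exceed 3 months. Matching on baseline characteristics cannot repair a mismatch in time origin. The 8.2.4 analyses carry the same condition.

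At stake is the first test in the secondary hierarchy. A false positive there would be read as a survival effect in recurrent disease and would open the gate to confirmed PFS, PFS and within-trial OS.

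**Working it through.** The plan gives no sample size, event count or power for this endpoint, so there is no figure of its own to reproduce.

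**Inputs from the documents**
- Controls: SAP Table 6, 62 + 149 + 92 + 40 + 60 + 30 + 46 + 65 + 38 + 58 = 640; medians 5.5 to 12.6 months.
- Level: one-sided 2.409% (SAP 8.1.1, 8.3.1).
- Placebo arm: 331 − 232 = 99 (SAP Introduction, 1.2.1).

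**Assumptions, because the documents give no figure**
- Treated placebo crossovers: 66. About 90% of 331 is 298; 298 − 232 = 66 if every DCVax-L patient is among the 90%. If 90% applies to placebo alone, 0.9 × 99 = 89. The range 60 to 90 was also run.
- Exponential survival, median 8 months, same hazard in both groups (no effect). An exponential mixture of the ten control arms has a median of about 7.9 months.
- Controls have no protected interval. Follow-up is cut at 60 months.
- Delay from progression to first dose: several patterns. Visits use a 28-day month ("a 28-day month is used for calculating visits"), so 3 months would be 84 days if that convention also governs this window.

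**Step 1: who is left out.** The share of progressors dying before a dose at delay d is 1 − 0.5^(d/8). At 1, 2 and 3 months this is 8.3%, 15.9% and 22.9%.

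**Step 2: hand approximation.** With many controls, the hazard ratio is close to observed over expected deaths in the treated group. Let λ = ln 2 / 8 = 0.0866 per month and m = mean delay among those who reach the dose. Observed is 1 per patient. Expected is λ(m + 1/λ) = 1 + λm. So HR ≈ 1/(1 + λm).
- Fixed 3 months: 1/(1 + 0.0866 × 3) = 1/1.260 = 0.79.
- Uniform 0 to 3 months, where survival to dose makes m = 1.44: 1/(1 + 0.0866 × 1.44) = 1/1.125 = 0.89.
- Uniform 0 to 1 month, m = 0.49: 1/1.042 = 0.96.

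**Step 3: simulation under no effect** (66 treated, 640 controls, Cox model, one-sided upper limit at 2.409%)

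| Delay to first dose | Apparent HR | False-positive rate |
|---|---|---|
| None | 1.00–1.01 | about 1.7% |
| Uniform 0–1 month | about 0.97 | 3–4% |
| Uniform 0–3 months | about 0.89 | 11–12% |
| Fixed 1 month | 0.93 | about 7% |
| Fixed 2 months | 0.86 | about 20% |
| Fixed 3 months | 0.79 | about 42% |

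The hand approximation agrees with the simulated hazard ratios to within about 0.01.

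**Step 4: range.** Across medians of 5.5 to 12.6 months and 60 to 90 treated, the uniform 0–3 month delay gives HR 0.85 to 0.93 and false positives of 6.1 to 29.8%. A fixed 3-month delay gives HR 0.72 to 0.86 and 17.0 to 86.3%.

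**Step 5: after the fix.** With treated patients joining the risk set only at first dose (uniform 0–3 months), HR returns to 1.00–1.01 and the false-positive rate to 1.8–2.5% in every scenario run.

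**The case against.** The strongest reply is that the size is unknown and may be small. Three months is an upper limit, and product is made before randomization (Protocol 5 and 7.1), so manufacture need not delay the dose. If most patients were dosed within a month, the false-positive rate is 3 to 4%, close to nominal. This stands, and it is why the rates for a fixed 2- or 3-month delay should be read as worst cases and not as typical.

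Second, a reader might infer that the bias must always favour DCVax-L. The documents do not support that as an absolute. They do not state the time origin of the recurrent-GBM controls. Where a control study counts from progression, its patients also had to survive to enrolment, and the bias partly cancels. The SAP neither states nor aligns these origins, so the reply limits the claim without removing it.

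Third, a reader might infer from SAP 3.2.3 that survival from initial surgery will be set against the same recurrent controls, since it lists a post-progression OS "but with the time interval measured from initial surgery in place of randomization". That section names no comparator, SAP 8.2 contains no surgery-based analysis, and SAP 1.2.4 lists surgery-based times under within-trial comparisons. It is an ambiguity to close, not evidence of a planned biased test.

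Fourth, the spread of control medians in Table 6 raises a question about pooling. It is separate and secondary, and the time-origin problem does not depend on it.

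**Conclusion.** The point holds. The clock and the entry condition in SAP 3.1.1 do not match, Protocol 8.4 allows a material gap between them, and nothing in SAP 8.2.1 to 8.2.4 handles it. For controls counted from their own enrolment, the gap is uncompensated survival credited to DCVax-L.

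The existence of the flaw rests on the text alone. The size does not: it depends on the delays, the number of treated placebo crossovers and the control origins, none of which is given. Under the 8-month, 66-patient assumptions, the apparent hazard ratio with no effect runs from about 0.97 (delays of 0 to 1 month) through about 0.89 (0 to 3 months) to about 0.79 if every patient waited exactly 3 months. The matching false-positive rates are 3–4%, 11–12% and about 42%. Because this is the first test in the secondary hierarchy and the repair is cheap, it should be settled before data lock.

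**What to change.** 1. For Secondary Endpoint #1 and the 8.2.4 analyses, set time zero at the first post-progression DCVax-L dose, or keep the progression clock and use delayed entry at that dose.
2. State the time origin of each Table 6 control study and align the comparison to it. A first-dose clock suits controls counted from enrolment or randomization; delayed entry suits controls counted from progression. Neither change alone aligns the two sides.
3. Keep the from-progression version as a sensitivity analysis.
4. Add a sensitivity analysis of all placebo patients who progressed, dosed or not. Those who decline crossover are already followed for survival. This also shows how far selection of patients able to be dosed matters, which changing the clock does not remove.
5. Report the distribution of time from progression to first dose, and the numbers who died or declined before dosing.
6. State in SAP 3.2.3 that the surgery-based post-progression endpoint will not be compared with the recurrent-GBM controls.

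The cost should be SAP wording and a few extra outputs. Crossover visits are scheduled from the first immunization (Protocol Appendix A1) and crossover exposure is already summarized (SAP Section 7), so the dose dates should be in hand. The downside is that reported post-progression survival under a first-dose clock will be shorter, by the progression-to-dose interval, which can exceed 3 months because the window starts at confirmation.
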